6 ANALYSIS POPULATIONS

The following populations will be identified:

• Intent to Treat Population (ITT): All patients randomized into the clinical trial, regardless of compliance.

¹ During study accrual, a new WHO classification system for CNS tumors was published [1]. Though the classification system in use at the time of study activation was used throughout the conduct of the study, the classification of all patients under the new WHO 2021 system will also be described.

- Safety Population: All patients who received at least one dose of BMX-001 or temozolomide
- Treated Population: All patients who completed chemoradiation with or without BMX-001. BMX-001 must be given for at least 6 weeks (or 13 doses).
- PK Population: Subjects who participated in the PK portion of the study (n=6).

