8.1 ENDPOINT

The study's primary endpoint is overall survival (OS) which is defined by the time between randomization and death, or the last follow-up if the patient remains alive.

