8.2 METHOD OF PRIMARY ENDPOINT ANALYSIS

This study will assess the hypothesis that BMX-001, when added to standard RT and TMZ, will sensitize the malignancy and result in enhanced patient survival as well as protect normal tissues from RT, resulting in better quality of life.

The primary analysis of survival will be done with the ITT population.

Kaplan-Meier methods will be used to graphically describe the distribution of overall survival (OS) among patients within the BMX-001 treatment group (Arm A) and within the control group (Arm B). Median OS, as well as 6-, 12-, 24-, and 36-month estimates of OS will be estimated from the Kaplan-Meier curve. A logrank test will compare arms with respect to the survival outcome.

As an additional descriptive statistic, the mean overall survival over a time interval chosen to maintain reasonable coverage of observed survival will be calculated.

If the underlying assumptions for the planned analyses are not satisfied, alternative methods of analysis depending on the observed distribution of the data will be explored.

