8.5 ADDITIONAL ANALYSES, INCLUDING SUBGROUP ANALYSES

The analyses described in Section 8.2 will be repeated within the treated population.

Within the ITT and treated patient populations, various subgroups analyses will be conducted. Subgroups will be defined by the following factors:

- Original histologic WHO grade (III or IV)
- New histologic WHO grade (III or IV)
- MGMT (present or absent)
- IDH status
- 19q FISH
- Age: subjects > 65 at time of consent
- Others as needed

The Kaplan-Meier estimator will describe the survival within each combination of histologic grade and treatment arm. Several analyses may be conducted:

1. Within each subgroup defined by the variables above, Cox proportional hazards model will assess the effect of treatment on survival.

- The Cox model will explore the joint effect of the clinical predictor and treatment assignment, and possibly their interaction. Such an analysis will explore whether the effect of BMX-001 treatment is consistent across levels of the clinical predictors.
- 3. The Cox model may also explore the joint effects of age, gender, histologic grade, MGMT, and other prognostic factors on survival.

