12.1 ENDPOINT

Progression-Free Survival (PFS) is defined as the time between initiation of protocol treatment and disease progression or death. If the patient remains alive without disease progression, then PFS will be censored at last follow-up. Analyses similar to those described for OS will be generated for PFS.

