12.2 METHOD OF ANALYSIS

The primary analysis of PFS will consider all patients, and consider them in their assigned treatment arm regardless of compliance. This approach to analysis is consistent with an intent-to-treat analysis approach.

As with survival, Kaplan-Meier methods will be used to graphically describe the distribution of PFS among patients within the BMX-001 treated group (Arm A) and within the control group (Arm B). Median PFS, as well as 6- and 12-month estimates of PFS will be estimated from the Kaplan-Meier curve. A logrank test will compare arms with respect to the PFS outcome.

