12.3 ADDITIONAL ANALYSES

Analyses similar to those described in Section 8.5 will be conducted for PFS, including analyses within subgroups of patients defined by grade, histological subtype, and tumor markers which have been captured in the study database. Analyses will also explore the interaction between clinical factors and treatment assignment on the PFS outcome.

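### OS and PFS in the Treated Population are conditional on completing chemoradiation but are still timed from randomisation or treatment start, so their medians and fixed-time rates read too high

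*SAP*

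**What the plan says.** The Treated Population in SAP 6 is "All patients who completed chemoradiation with or without BMX-001", with a further minimum exposure to BMX-001 of 6 weeks or 13 doses that in practice applies only to Arm A.

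SAP 8.1 sets the primary endpoint as "overall survival (OS) which is defined by the time between randomization and death". SAP 8.2 lists the statistics: "Median OS, as well as 6-, 12-, 24-, and 36-month estimates of OS will be estimated from the Kaplan-Meier curve", together with a log-rank test and a mean survival over a chosen interval. SAP 8.5 then states: "The analyses described in Section 8.2 will be repeated within the treated population".

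PFS in SAP 12.1 is "defined as the time between initiation of protocol treatment and disease progression or death". SAP 12.2 gives its statistics: "Median PFS, as well as 6- and 12-month estimates of PFS will be estimated from the Kaplan-Meier curve". SAP 12.3 carries the additional analyses across: "Analyses similar to those described in Section 8.5 will be conducted for PFS". The table list in SAP 19 names both ITT and Treated for OS and for PFS.

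Neither document sets a landmark, uses delayed entry, or labels the Treated results as conditional on completion. SAP 18 allows sensitivity analyses on including or excluding patients, but these would not change the time origin.

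**The concern.** Membership of the Treated Population is settled by something that happens after the clock starts. A patient who dies in week 4 of radiotherapy is removed retrospectively, while everyone who stays in is counted as at risk from day 0. The early part of the curve is therefore flat by construction in both arms, and every later point is raised.

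What is at stake is the absolute figures. The Treated medians and 6-, 12-, 24- and 36-month rates would stand next to the ITT ones with the same endpoint definition. SAP 8.4.1 says that the trial is to decide whether BMX-001 merits further investigation, and absolute survival figures are likely to be read in that decision. The problem is separate from the Arm A exposure minimum: deleting that rule would leave it in place.

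**Working it through.** **Inputs**
- Grade medians of 14.6 months (IV) and 36 months (III): SAP 8.4.1.
- 20% grade III; control and target medians of 18.9 and 30.0 months; HR 0.63; one-sided 0.2; 90% power; 84 deaths: SAP 8.4.2.
- Chemoradiation of 6 weeks (SAP 4), in less than seven weeks (Protocol 9.1.8.1).
- Gap from randomisation to treatment start: not stated. Assumed 0 to 21 days, from the screening window in Protocol 13.1.

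Time from randomisation to completion, t0, therefore runs from 42 days (42/30.44 = 1.38 months) to 49 + 21 = 70 days (2.30 months).

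**The plan's own figures reproduce**
- 0.8 × 14.6 + 0.2 × 36 = 18.88, stated as 18.9. 18.9/0.63 = 30.0.
- Schoenfeld's formula gives 84.5 deaths, and 84 deaths give power 0.899.

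These figures are not in dispute and only supply the survival curves. The 18.9 is a weighted average of two medians. The median of the 80/20 mixture itself is 17.1 months, which is used below.

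**Effect of the entry rule**

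For a set restricted to patients alive at t0, the Kaplan-Meier curve from the original origin estimates S(t)/S(t0) for t > t0, which is never below S(t).

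S(t) = 0.8 × 2^(−t/14.6) + 0.2 × 2^(−t/36)

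S(6) = 0.780, S(1.38) = 0.944 and S(2.30) = 0.909. So 6-month OS becomes 0.780/0.944 = 0.826 to 0.780/0.909 = 0.858.

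| OS with no drug effect | All patients | Treated, t0 = 1.38 | Treated, t0 = 2.30 |
|---|---|---|---|
| 6 months | 78% | 83% | 86% |
| 12 months | 61% | 65% | 67% |
| 24 months | 38% | 40% | 42% |
| 36 months | 24% | 26% | 27% |
| Median (months) | 17.1 | 18.5 | 19.5 |

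Under the SAP's single exponential, the median among completers is m + t0. At 6 weeks that is 18.9 + 1.4 = 20.3 in Arm B and 30.0 + 1.4 = 31.4 in Arm A.

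**Lower early hazard**

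Suppose deaths before t0 run at a fraction f of the exponential rate, with the overall median held at m. The excess on the median is then (m − t0) × x/(1 − x), where x = f × t0/m. For m = 18.9:
- t0 = 1.38: 0.7 months at f = 0.5 and 0.3 at f = 0.25.
- t0 = 2.30: 1.1 months at f = 0.5 and 0.5 at f = 0.25.
- f = 0: no excess.

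**Comparison between arms**

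In 1,000 simulated trials (160 patients, 27 months' accrual, cut at 84 deaths, t0 = 6 weeks), the typical hazard ratio was 0.643 both in all patients and in completers.

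**Which remedy works**

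With the same mixture and completion spread uniformly over 1.5 to 2.3 months:
- All patients from randomisation: 6-month OS 78.0%, median 17.1 months.
- Treated as planned: 84.4%, 19.1 months.
- Treated with delayed entry at completion: 83.1%, 18.7 months.
- Treated with the clock reset to completion: about 78%, about 17.2 months.

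Delayed entry removes only (84.4 − 83.1)/(84.4 − 78.0), about one fifth, of the excess in the 6-month rate. Nobody is at risk before the first completion, so the left-truncated curve cannot recover the missing early deaths and returns nearly S(t)/S(t0).

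**The case against.** The strongest reply is that survival from randomisation among completers is a legitimate description. SAP 6 openly defines the set as completers, SAP 19 lists results by named population, and these analyses sit under additional analyses. No decision rule uses them: primary OS is ITT (SAP 8.2) and primary PFS takes all patients as assigned (SAP 12.2). All of this stands, and it limits the reach of the point. It does not supply the missing label or time origin.

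It can also be said that a constant hazard from day 0 overstates early deaths. Entry requires KPS of at least 70, a definitive resection and little residual enhancement (Protocol 5.5.1), and at least 2 weeks since surgery before treatment (Protocol 9.1.3). This also stands, and for that reason the figures above are at the upper end.

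Four stronger readings are tempting, and the documents do not support them.
- **That the Treated comparison of arms is biased by this mechanism.** No deaths fall in the guaranteed period in either arm, so equal guaranteed time leaves the log-rank test and hazard ratio unchanged. Unequal selection into the set is a different question.
- **That PFS is inflated by a known amount.** Applying the same formula to assumed PFS medians of 5 to 12 months with 6 weeks to completion gives 6 to 9 points at 6 months. The documents give no PFS median, and completion guarantees only being alive: neurological worsening can count as progression in someone who completes (Protocol 13.8.4). The first post-baseline MRI comes 2 to 4 weeks after radiotherapy, so few progressions can be dated earlier in any population. Such a figure is at most a ceiling.
- **That the plan compares Treated medians with 14.6 and 36 months.** Those are power inputs, and no such comparison is planned.
- **That this set supported the breakthrough application.** SAP 8.3.2 speaks of treated subjects but does not say whether that is the section 6 population.

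**Conclusion.** The point holds for the absolute OS and PFS figures in the Treated Population. As planned, they are conditional on completing chemoradiation while carrying an unconditional time origin, so they overstate survival from that origin in both arms.

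For OS the excess is at most about 5 to 8 points at 6 months and about 1.4 to 2.4 months on the median. This rests on the SAP's grade medians, exponential survival within grade, 20% grade III, and 1.4 to 2.3 months from randomisation to completion, the upper end of which includes an assumed gap of up to 21 days. If early deaths run at half that rate, the median excess is about 0.7 months at 6 weeks to completion and 1.1 months at the longest interval. It is zero if nobody dies before completing. For PFS only the direction can be stated.

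The primary ITT analyses of OS and PFS are untouched. The change is worth making because it is cheap and alters figures that will be reported, not because a trial conclusion depends on it.

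**What to change.** In SAP 8.5, 12.3 and 19, for the Treated Population only:
- Start OS and PFS at the date chemoradiation is completed, and state how that date is defined.
- For PFS, include only patients alive and progression-free on that date.
- Label the results as conditional on completing chemoradiation, and not comparable with the ITT figures or with the historical medians in SAP 8.4.

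Delayed entry from the original origin is not an adequate substitute, for the reason shown in the working.

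The cost is a few sentences in the SAP and one date variable in the existing programs. No new data are needed and the ITT analyses do not change. The downside is that Treated-set figures become lower and have a different time origin from ITT. The Arm A exposure minimum is a separate matter that this change does not address.

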7 TREATMENT AND SUBJECT DISPOSITION

A CONSORT diagram will be generated that displays the number of patients randomized within each treatment arm, the number of patients within each arm who are treated with chemoradiation, as well as the number of cycles of adjuvant treatment received. For treatment during chemoradiation, the total dose of BMX-001 administered will be summarized, as well as the total dose of TMZ and RT administered.

All subjects who withdrew or were withdrawn from the study will be listed by treatment arm with the reason for withdrawal.

8 PRIMARY OBJECTIVE: SURVIVAL

The primary goal of this randomized, open-label Phase 2 study is to examine the impact of BMX-001 on overall survival among patients newly diagnosed with HGG who are receiving SOC treatment consisting of daily TMZ and RT. After the primary endpoint analysis at 84 deaths, we will continue following patients for survival and disease progression even after the primary endpoint analysis. Per protocol, patients will be followed indefinitely.

8.1 ENDPOINT

The study's primary endpoint is overall survival (OS) which is defined by the time between randomization and death, or the last follow-up if the patient remains alive.

8.2 METHOD OF PRIMARY ENDPOINT ANALYSIS

This study will assess the hypothesis that BMX-001, when added to standard RT and TMZ, will sensitize the malignancy and result in enhanced patient survival as well as protect normal tissues from RT, resulting in better quality of life.

The primary analysis of survival will be done with the ITT population.

Kaplan-Meier methods will be used to graphically describe the distribution of overall survival (OS) among patients within the BMX-001 treatment group (Arm A) and within the control group (Arm B). Median OS, as well as 6-, 12-, 24-, and 36-month estimates of OS will be estimated from the Kaplan-Meier curve. A logrank test will compare arms with respect to the survival outcome.

As an additional descriptive statistic, the mean overall survival over a time interval chosen to maintain reasonable coverage of observed survival will be calculated.

If the underlying assumptions for the planned analyses are not satisfied, alternative methods of analysis depending on the observed distribution of the data will be explored.

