# **5 PROTOCOL SYNOPSIS**

### 5.1 Purpose

This is a Phase 1/2 study of BMX-001 in combination with standard radiation therapy (RT) and temozolomide (TMZ) in the treatment of newly diagnosed high grade glioma (HGG) patients. Phase 1 was conducted as a single site study at the Preston Robert Tisch Brain Tumor Center at Duke (PRT-BTC). Phase 2 will be conducted as a multi-center study and will include up to 10 additional sites besides the PRT-BTC at Duke.

## 5.2 Phase 1

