#### 9.1.9 Randomization

Within the Phase 2 portion of this study, patients will be randomized using a 1:1 allocation ratio to receive standard of care treatment consisting of TMZ and RT with BMX-001 (Arm A) or without BMX-

001 (Arm B). A permuted block randomization algorithm stratified by grade (III / IV) and by institution will be used.

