#### 16.5.5.1 **Power of Survival Comparisons**

The primary goal of the Phase 2 portion of this study is to assess the effect of BMX-001 treatment in conjunction with standard of care treatment consisting of temozolomide and radiation on the survival of patients newly diagnosed with grade III or IV glioma. A permuted block randomization stratified by histologic grade (grade III / IV) and institution will be used to assign patients to treatment with or without BMX-001.

With standard treatment, the median survival of Grade IV patients is 14.6 months, and the median survival of Grade III is approximately 36 months. Given that we anticipate that approximately 10% of patients to be Grade III, we estimate that the overall median survival with standard treatment to be roughly 16.7 months.

Though this Phase 2 study is comparative, the goal is to determine whether BMX-001 is worthy of further investigation in combination with standard RT and TMZ treatment, and not to make definitive statements about the effect of BMX-001. Many aspects of the new treatment will be considered in the decision-making concerning further investigation, including relative toxicity and ease of treatment administration. As a Phase 2 study, there is a need to constrain the sample size requirements at the expense of either an increased false negative or false positive rate. A false-positive rate of 0.2 will be used to test the primary statistical hypothesis while maintaining reasonably high power [80-82].

The power of a statistical comparison of survival is a function of the number of deaths observed. In order that a 1-tailed logrank test conducted at the 0.2 level to have 90% power to detect a hazard ratio of 0.63, 84 deaths need to be observed among the 160 randomized patients. Under the assumption that survival is exponentially distributed, this hazard ratio represents an increase in median survival from 16.7 to 26.5 months.

With an accrual goal of 160 patients and an expected randomization rate of approximately 6 patients per month, we anticipate that accrual will be completed within approximately 27 months. It is estimated that approximately 10 months after accrual completion are needed to observe approximately 84 deaths among randomized patients.

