4 OVERVIEW OF STUDY DESIGN

The Phase 2 portion of this protocol is a multicenter randomized open-label study comparing the impact of concurrent daily Temozolomide (TMZ) and Radiation Therapy (RT) with BMX-001 (Arm A) versus concurrent daily TMZ and RT alone (Arm B) on survival in patients among patients with newly diagnosed high grade glioma (HGG - WHO grade III and IV). Subjects were randomized with a treatment arm allocation ratio

TREATMENT ARMS

Arm A: Concurrent daily TMZ and RT with BMX-001

Arm B: Concurrent daily TMZ and RT alone

of 1:1, with a goal of enrolling 160 patients in this phase of the study (80 subjects per arm). A permuted block randomization stratified by histologic grade (grade III / IV) and institution will be used to assign patients to treatment with or without BMX-001.

Subjects in Arm A were administered BMX-001 subcutaneously first as a loading dose (28 mg) given 0 to 4 days before the start of chemoradiation and then at subsequent dose (14 mg) twice a week for eight weeks. Subjects in Arm A and Arm B received TMZ dosed at 75 mg/m² orally daily for 42 days and RT delivered in daily fractions of 1.8-2 Gy given 5 days a week for 6 weeks for a total of 59.4-60 Gy.

In all subjects, cognitive performance was measured at the time of enrollment and 2 weeks after the completion of RT, and standard of care (SOC) clinic visits (approximately 8 weeks apart +/- 2 weeks) until death, or patient's choice to discontinue study measures. Cognitive testing was to continue after noted progression until the 12 month follow up timepoint is reached.

In order to characterize the repeated dose pharmacokinetic (PK) profiles of BMX-001 in combination with RT and TMZ in newly diagnosed HGG patients, PK blood samples were drawn on Days 8 and 36 only from the first 6 patients enrolled and assigned to Arm A at a single center (Duke). Measures were obtained at approximately the following times: Pre-

dose, then 0.5 hour, 1 hour, 2 hours, 6 hours and 24 hours post-dose. Samples will be analyzed for BMX-001 using validated analytical methods at the Duke PK lab.

The study's primary phase 2 endpoint is overall survival (OS), defined as the time between randomization and death. A logrank test will be used to compare the survival experience of the two treatment arms. An intent-to-treat philosophy will be used in the analysis of survival by including all patients who are randomized in the analysis. Other analysis sets are defined in this document.

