8.4.1 ORIGINAL POWER ANALYSIS

With standard treatment, the median survival of Grade IV patients is 14.6 months, and the median survival of Grade III is approximately 36 months. Before study activation, we anticipated that approximately 10% of patients to be Grade III. With 10% of patients as grade III, we estimated that the overall median survival with standard treatment to be roughly 16.7 months

Though this Phase 2 study is comparative, the goal is to determine whether BMX-001 is worthy of further investigation in combination with standard RT and TMZ treatment. Many aspects of the new treatment will be considered in the decision-making concerning further investigation, including relative toxicity and ease of treatment administration. As a Phase 2 study, there is a need to constrain the sample size requirements at the expense of either an increased false negative or false positive rate. A false-positive rate of 0.2 will be used to test the primary statistical hypothesis while maintaining reasonably high power [3-5].

The power of a statistical comparison of survival is a function of the number of deaths observed. In order that a 1-tailed logrank test conducted at the 0.2 level to have 90% power to detect a hazard ratio of 0.63, 84 deaths need to be observed among the 160 randomized patients. Under the assumption that survival is exponentially distributed, this hazard ratio represents an increase in median survival from 16.7 to 26.5 months.

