8.4.2 REVISED POWER ANALYSIS

In actuality, approximately 20% of patients enrolled were Grade III. With 20% of patients to be grade III, we estimate that the median overall survival with standard of care treatment to be roughly 18.9 months.

With these modifications the power analysis has been revised:

The power of a statistical comparison of survival is a function of the number of deaths observed. In order that a 1-tailed logrank test conducted at the 0.2 level to have 90% power to detect a hazard ratio of 0.63, 84 deaths need to be observed among the 160 randomized patients. Under the assumption that survival is exponentially distributed, this hazard ratio represents an increase in median survival from 18.9 to 30.0 months.

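### The primary OS logrank ignores grade, a randomisation factor with expected medians of 14.6 v about 36 months; stratifying by grade is a cheap improvement

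*SAP*

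**What the plan says.** Randomisation uses grade as a factor. Protocol 9.1.9: "A permuted block randomization algorithm stratified by grade (III / IV) and by institution will be used". SAP 4 agrees: "A permuted block randomization stratified by histologic grade (grade III / IV) and institution will be used to assign patients". Block size is not stated. Protocol 5.1 says Phase 2 "will include up to 10 additional sites besides the PRT-BTC at Duke".

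The primary test does not use grade. SAP 8.2: "A logrank test will compare arms with respect to the survival outcome". Protocol 16.5.1.2 has the same sentence, and the summaries in Protocol 5.7 and SAP 4 also describe a plain logrank. SAP 8.2 allows alternative methods only if assumptions fail, and it names no stratified test.

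The SAP treats grade as strongly prognostic. Section 8.4.1 states that "the median survival of Grade IV patients is 14.6 months, and the median survival of Grade III is approximately 36 months". Section 8.4.2 adds: "In actuality, approximately 20% of patients enrolled were Grade III". It raises the expected control median from 16.7 to 18.9 months for that reason.

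Grade does enter elsewhere. SAP 5 tabulates it by arm. SAP 8.5 commits to subgroup analyses that include the original WHO grade, and says: "The Kaplan-Meier estimator will describe the survival within each combination of histologic grade and treatment arm". It also lists Cox models with treatment and clinical predictors among analyses that may be done. None of these is the primary test.

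**The concern.** When a factor is strong enough to stratify the randomisation and to move the design median, the primary test would normally account for it. There are two consequences if it does not.

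First, balancing the arms on a prognostic factor reduces the true variability of the test statistic. The unstratified variance does not credit this, so the test is slightly conservative and slightly less powerful.

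Second, the blocks run within grade-by-institution cells. With up to 11 sites and about 32 grade III patients, many cells will hold incomplete blocks, and some grade difference between arms can remain. An excess of grade III patients in Arm A then favours BMX-001 whatever the drug does, and an excess in Arm B works against it. The plan will be applied to one trial with one realised split, and the test already runs at a one-sided 0.2.

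**Working it through.** **The plan's own figure.** SAP 8.4.1 asks for 84 deaths for 90% power at a hazard ratio of 0.63, one-sided 0.2. By Schoenfeld's formula with 1:1 allocation:

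- Deaths = 4(z0.8 + z0.9)² / ln(0.63)² = 4(0.842 + 1.282)² / 0.2135 = 84.5.
- Power at exactly 84 deaths is 0.899. The stated 84 is reproduced.

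**Strength of grade.** Under exponential survival, the grade IV to grade III hazard ratio is 36 / 14.6 = 2.47.

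**Simulation set-up.** The plan supplies 160 patients, accrual at 6 per month (160 / 6 = 26.7 months), control medians of 14.6 and 36 months, 20% grade III, a data cut at the 84th death and a one-sided 0.2 test. Survival is exponential within grade, and the within-grade hazard ratio is 1 or 0.63. The number of sites, their sizes and the block size are assumptions. There were 20,000 runs per scenario, with a Monte Carlo standard error of about 0.3 points.

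**Averaged over randomisations** (11 equal sites with blocks of 2, 4 or 6; 5 equal sites with blocks of 4):

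| | Unstratified | Stratified by grade |
|---|---|---|
| Type I error | 0.195-0.198 | 0.200-0.202 |
| Power at HR 0.63 | 0.888-0.893 | 0.895-0.900 |

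The power loss is 0.5-0.8 points. The two tests reach different conclusions in 3.7-4.6% of trials under no effect and in 2.3-2.8% at HR 0.63. A separately coded simulation, using blocks of 4 and 10% or 20% grade III, put the gain from stratifying at 0.2-0.9 points.

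**Given the realised split** (0.20 × 160 = 32 grade III patients, 80 per arm):

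| Grade III, Arm A v Arm B | Unstratified type I error | Unstratified power |
|---|---|---|
| 20 v 12 | 0.308 | 0.944 |
| 18 v 14 | 0.247 | 0.920 |
| 16 v 16 | 0.190 | 0.892 |
| 14 v 18 | 0.151 | 0.847 |
| 12 v 20 | 0.104 | 0.802 |

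The stratified test stays at 0.196-0.205 for type I error and 0.891-0.898 for power across all five splits.

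**How often such splits occur.** The first two result columns fix 32 grade III patients. In the last column each patient is grade III with probability 0.2. Sites are equal in size.

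| Sites, block size | Difference ≥4, total fixed | Difference ≥8, total fixed | Difference ≥4, total random |
|---|---|---|---|
| 5, 2 | 4% | 0% | not run |
| 5, 4 | 13% | 0.01% | 8-9% |
| 11, 2 | 19% | 0.1% | 13% |
| 11, 4 | 32% | 2% | 25% |
| 11, 6 | 43% | 6.5% | 36-37% |

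About half of the differences favour each arm. The fixed-total figures are higher partly because an even total permits only even differences. With random, unequal site sizes as well (11 sites, blocks of 4), a difference of 4 or more occurs in about 21% of trials. With blocks of 4 stratified by grade alone, it did not occur. The exposure therefore comes from crossing grade with institution.

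**The case against.** No operating characteristic in the plan is wrong. The logrank is valid after stratified randomisation, average type I error and power are within about a point of the stated values, and the trial is a Phase 2 screen intended "not to make definitive statements about the effect of BMX-001". SAP 8.5 supplies grade-specific survival results, and SAP 5 would make any imbalance visible. All of this stands and limits the weight of the point. It does not change which test decides the trial.

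The conditional figures can look more alarming than they are. A type I error of 0.308 needs an Arm A excess of 8 grade III patients; an excess that large or larger arises in about 0.6-1.1% of trials with 11 sites and blocks of 4. Differences of 4 are the realistic case, and their frequency depends on inputs that the documents do not give.

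The strongest objection concerns timing. SAP 8.3.1 and 8.3.2 report deaths by arm at two looks, the second unplanned. Changing the primary test afterwards invites the charge that the choice followed the data, and the two tests can disagree. The documents do not say whether either look examined survival by grade and arm. This is a reason to document the change carefully and make it before the 84-death analysis. It is not a reason to leave the test as it is.

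**Conclusion.** The point holds as a low-cost improvement. The primary test omits a strongly prognostic randomisation factor. On average this costs less than one point of power and makes the test very slightly conservative. For a grade III difference of 4 between arms, the unstratified test runs at about 0.25 or 0.15 where 0.20 was intended, or at about 85% power where 90% was intended, depending on direction. The stratified test is essentially unaffected. Such differences might occur in anything from 4% to 43% of trials over the site numbers and block sizes examined.

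These results assume exponential survival within grade, the plan's medians, a common hazard ratio in both grades and 20% grade III. The absence of strata is certain from the text; the practical importance is modest and depends on the realised split.

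**What to change.** Amend SAP 8.2 so that the primary test is a one-sided 0.2 logrank stratified by grade (III or IV).

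- Use the grade recorded at randomisation under the enrolment classification. SAP 6, footnote 1, also introduces WHO 2021 grades, so the amendment should say which applies.
- Do not stratify the test by institution; the strata would be too sparse.
- If a hazard ratio is reported, which SAP 8.2 does not currently plan, take it from a Cox model stratified by the same grade.
- Keep the unstratified logrank as a named sensitivity analysis.
- Apply the same approach to PFS in SAP 12.2 for consistency. The documents give no PFS medians by grade, so the gain there has not been calculated.

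Date the amendment before the 84-death analysis and state that no grade-stratified result by arm informed it. If that statement cannot truthfully be made, disclose what was seen. In that case, keeping the present test as primary and adding the stratified test as a prespecified sensitivity analysis is the safer course.

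The cost is a short amendment with its justification, and no new patients or data. SAP 8.2 would then differ from Protocol 16.5.1.2, but SAP 3 gives the SAP precedence.
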